12.5 Common Terminology Criteria for Adverse Events

The descriptions and grading scales found in the revised NCI CTCAE v4.0 will be utilized for AE reporting. (<http://ctep.cancer.gov/reporting/ctc.html>).

12.6 Abbreviations

Abbreviation/Term	Definition
AE	adverse event
ADA	anti-drug antibodies
ASaT	All Subjects as Treated
BICR	Blinded Independent Central Review
CA 125	cancer antigen 125
CD	carboplatin plus pegylated liposomal doxorubicin
CI	confidence interval
CP	carboplatin plus paclitaxel
CR	complete response
CSR	clinical study report
CT	computed tomography
CTCAE	Common Toxicity Criteria for Adverse Events
CTLs	cytotoxic t lymphocytes cells
CTLA-4	cytotoxic t-lymphocyte-associated antigen-4
DCR	disease control rate
DOR	duration of response
ECG	electrocardiogram
ECI	events of clinical interest
ECOG	Eastern Cooperative Oncology Group
EDC	electronic data capture
eCRFs	electronic case report forms
EOC	epithelial ovarian cancer
ERC	Ethics Review Committee
FAS	Full Analysis Set
FBR	future biomedical research
FDAAA	Food and Drug Administration Amendments Act
FDAMA	Food and Drug Administration Modernization Act
FSH	follicle-stimulating hormone
GCIG	Gynecologic Cancer InterGroup
GCP	Good Clinical Practice
GEP	gene-expression profile
HGSC	high-grade serous carcinoma
HIV	human immunodeficiency virus
HR	hazard ratio
ICH	International Conference for Harmonization
IgG4	immunoglobulin g4
IHC	immunohistochemistry
IP	intraperitoneal
irAEs	immune-related adverse events
irRECIST	Immune-related Response Evaluation Criteria in Solid Tumors
IRB	Institutional Review Board
IUD	intrauterine device
IV	intravenous
IVRS	interactive voice response system
IWRS	integrated web response system
KM	Kaplan-Meier
KN	KEYNOTE
LMP	last menstrual period

Abbreviation/Term	Definition
mAb	monoclonal antibody
MRI	magnetic resonance imaging
MSD	Merck Sharp & Dohme Corp., a subsidiary of Merck & Co., Inc.
NCI	National Cancer Institute
NPV	negative predictive value
NSCLC	non-small cell lung cancer
ORR	overall response rate
OS	overall survival
OTC	over-the-counter
PBPK	physiologically-based pharmacokinetic
PD	progressive disease
PD-1	programmed cell death protein 1
PD-L1	program cell death-ligand protein 1
PD-L2	program cell death-ligand protein 2
PFI	platinum-free interval
PFS	progression-free survival
PK	pharmacokinetic
PLD	pegylated liposomal doxorubicin
PPV	positive predictive value
PR	partial response
Q2W	every 2 weeks
Q3W	every 3 weeks
Q9W	every 9 weeks
Q12W	every 12 weeks
RECIST	Response Evaluation Criteria in Solid Tumors
RNA	ribonucleic acid
ROC	recurrent ovarian cancer
SAC	Scientific Advisory Committee
SAE	serious adverse events
SD	stable disease
sSAP	supplemental Statistical Analysis Plan
TFI	treatment-free interval
TILs	tumor-infiltrating lymphocytes
TTR	time to recurrence
ULN	upper limit of normal

1. INTRODUCTION

This supplemental SAP (sSAP) is a companion document to the protocol. In addition to the information presented in the protocol SAP which provides the principal features of confirmatory analyses for this trial, this supplemental SAP provides additional statistical analysis details/data derivations and documents modifications or additions to the analysis plan that are not “principal” in nature and result from information that was not available at the time of protocol finalization.

2. SUMMARY OF CHANGES

PRIMARY REASON(S) FOR THIS AMENDMENT:

Section Number (s)	Section Title(s)	Description of Change (s)	Rationale
3.1	Statistical Analysis Plan Summary	Population of primary efficacy analysis changed to All Subjects as Treated (ASaT).	Per FDA requirement.
3.1	Statistical Analysis Plan Summary	Delete 95% CI for safety analysis.	For single arm study, 95% CI for AE incidence rate is not required.
3.4.1	Efficacy Endpoints	Reorganized.	To align with protocol section 3 Objectives.
8.4.1	Efficacy Endpoints	Updated definition of PFS	Editorial update
3.6.1	Statistical Methods for Efficacy Analysis	Censoring rules for DOR and PFS added.	To provide more details about censoring rule.
3.6.1	Statistical Methods for Efficacy Analysis	Added information regarding data cutpoint	To provide maximum flexibility to perform additional data analysis
3.11	Compliance	Section deleted.	Per new alignment.

3. ANALYTICAL AND METHODOLOGICAL DETAILS

3.1 Statistical Analysis Plan Summary

Key elements of the statistical analysis plan are summarized below; the comprehensive plan is provided in Sections 3.2-3.12.

Study Design Overview	A Phase II, open-label, single arm, two-cohort, multi-center trial of pembrolizumab monotherapy in subjects with advanced ovarian cancer who have demonstrated recurrent disease following the front line treatment and received up to 5 lines of treatments for ROC.
Treatment Assignment	
Cohort A will enroll subjects with ROC who have received 0-2 prior lines for treating ROC (i.e., 1-3 total prior lines counting the front line) and with a platinum-free interval or treatment-free interval of 3 to 12 months based on the last regimen received.
 
Cohort B will enroll subject with ROC who have received 3 to 5 prior lines for treating ROC (i.e., 4-6 total prior lines counting the front line) and with a platinum-free interval or treatment-free interval ≥ 3 months based on the last regimen received.
 
In both cohorts, subjects will be treated with pembrolizumab monotherapy 200 mg every 3 weeks (Q3W) as trial treatment by non-randomized assignment in an unblinded fashion.

Analysis Populations	
Efficacy: All Subjects as Treated (ASaT)
 
Safety: All Subjects as Treated (ASaT)

Primary Endpoint(s)	ORR by RECIST 1.1 per BICR review
Key Secondary Endpoints	
 • DOR, DCR, PFS per RECIST 1.1 as assessed by BICR • OS
Statistical Methods for Key Efficacy Analyses	The primary objectives will be evaluated by the point estimate and 95% confidence interval for the ORR in the Cohort A-All Comer Population and Cohort A PD-L1 _H subgroup, respectively, using an exact binomial distribution. ORR will be evaluated similarly in the Cohort B-All Comer group and Cohort B PD-L1 _H subgroup, respectively.
Statistical Methods for Key Safety Analyses	Summary statistics for the incidence rate of Grade 2 or higher adverse events with an immune etiology and the incidence rate of Grade 4/5 AEs.
Interim Analyses	An interim analysis is planned at 4 months after the first 100 subjects have been enrolled in Cohort A, which will be used as the training set. IA will evaluate clinical activity and the correlation of PD-L1 in tumor tissue samples in the training set to facilitate the PD-L1 expression cutoff selection.
Multiplicity	No multiplicity adjustment has been planned.

Sample Size and Power	Cohort A-All Comer group include all enrolled subjects of Cohort A. A minimum of 75 subjects will be enrolled for the subgroup with a PFI/TFI of 3-<6 months and a minimum of 75 subjects will be enrolled for the subgroup with a PFI/TFI of 6 to 12 months. The first 100 enrolled Cohort A subjects will be used as the training set for determining a PD-L1 expression cut point. The additional 150 enrolled Cohort A subjects will be in the confirmation set, therefore, the study will enroll approximately 250 Cohort A subjects regardless of the PD-L1 status. The exact number of subjects enrolled in the confirmation set will depend on the prevalence of the PD-L1 _H as determined by the biomarker analysis. Approximately 75 subjects will be enrolled in Cohort B.
-----------------------	--

3.2 Responsibility for Analyses/In-House Blinding

The statistical analysis of the data obtained from this study will be the responsibility of the clinical biostatistics department of the SPONSOR. This trial is being conducted as an open-label non-randomized single-arm clinical trial, i.e., subjects, investigators, and SPONSOR personnel will be aware of subject treatment assignments after each subject is enrolled and treatment is assigned. The study team at the Sponsor consisting of clinical, statistical, statistical programming and data management personnel, will be blinded to subject-level PD-L1 biomarker results. An unblinded Sponsor biomarker statistician will have access to the subject-level PD-L1 results for the purpose of data review and biomarker correlation analysis. The unblinded SPONSOR biomarker statistician will have no other responsibilities associated with the study.

3.3 Hypotheses/Estimation

Objectives of the study are stated in Section 3.0 of the protocol.

3.4 Analysis Endpoints

Efficacy and safety endpoints that will be evaluated are listed below.

3.4.1 Efficacy Endpoints

Primary

- **Objective response rate (ORR) - per RECIST 1.1 assessed by BICR**

Objective Response Rate (ORR), defined as the proportion of subjects in the analysis population who have confirmed complete response (CR) or partial response (PR) at any time during the study.

Secondary

- **Duration of Response (DOR) - per RECIST 1.1 assessed by BICR and by investigator**

Duration of response (DOR), defined as the time from first documented evidence of response to disease progression in subjects who achieve a confirmed PR or CR.

- **Progression-free Survival (PFS) - per RECIST 1.1 assessed by BICR and by investigator**

Progression-free survival (PFS), defined as the time from the first day of study treatment to the first documented disease progression or death due to any cause, whichever occurs first.

- **Overall survival (OS)**

Overall survival (OS), defined as the time from the first day of study treatment to death due to any cause.

- **Disease Control Rate (DCR) - per RECIST 1.1 assessed by BICR**

Disease Control Rate (DCR), defined as the percentage of subjects who have achieved confirmed CR or PR or have demonstrated SD for at least 24 weeks prior to any evidence of progression.

Exploratory

- **Progression-free survival (PFS) – irRECIST assessed by BICR**

Progression-free-survival (PFS) is defined as the time from first day of study treatment to the first confirmed disease progression or death due to any cause, whichever occurs first.

ORR and DOR per irRECIST by BICR are also the exploratory efficacy endpoints.

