7.1.2.6.6 RECIST 1.1 Assessment of Disease

RECIST 1.1 will be applied by the sites and the central imaging vendor as the primary measure for assessment of tumor response, date of disease progression, and as a basis for all protocol guidelines related to disease status (e.g., discontinuation of study therapy). Although

RECIST 1.1 references to maximum of 5 target lesions in total and 2 per organ, Merck allows maximum of 10 target lesions in total and 5 per organ.

7.1.2.6.7 irRECIST Assessment of Disease

irRECIST is RECIST 1.1 adapted as described below to account for the unique tumor response seen with immunotherapeutic drugs. irRECIST will be used by site investigator/local radiology review to assess tumor response and progression, and make treatment decisions. This data will be collected in the clinical database. Treatment efficacy based on irRECIST as assessed by central imaging vendor review will be evaluated retrospectively.

When feasible, subjects should not be discontinued from study treatment until progression is confirmed by the local site investigator/radiology assessment. This allowance to continue treatment despite initial radiologic PD takes into account the observation that some subjects can have a transient tumor flare in the first few months after the start of immunotherapy, and then experience subsequent disease response. The following may present as tumor flare:

- Worsening of existing target lesion(s)
- Worsening of existing non-target lesion(s)
- Development of new lesion(s)

In subjects who have shown initial evidence of radiological PD by RECIST 1.1, the investigator needs to decide whether to continue a subject on study treatment until repeat imaging is obtained (using irRECIST for subject management. See [Table 5](#)), which should be based on assessing subject's overall clinical condition, including performance status, clinical symptoms, and laboratory data. If the subject is clinically stable and can continue on study treatment, repeat scan should be performed ≥ 4 weeks later in order to confirm PD. Clinical stable status is defined as the following:

- 1) Absence of symptoms and signs indicating clinically significant progression of disease, including worsening of laboratory values
- 2) No decline in ECOG performance status
- 3) Absence of rapid progression of disease
- 4) Absence of progressive tumor at critical anatomical sites (e.g., cord compression) requiring urgent alternative medical intervention

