Any subject deemed clinically unstable should be discontinued from trial treatment at site-assessed first radiologic evidence of PD and is not required to have repeat imaging for PD confirmation.

In determining whether or not the tumor burden has increased or decreased per irRECIST, the investigator should consider all target and non-target lesions as well as any incremental new lesion(s).

Scenarios where PD is not confirmed at repeat imaging if ALL of the following occur by irRECIST:

- Target lesion sum of diameters is <20% or <5 mm absolute increase compared to nadir
- Non-target disease resulting in initial PD is qualitatively stable or improved
- New lesion resulting in initial PD is qualitatively stable or improved
- No incremental new lesion(s) since last evaluation
- No incremental new non-target lesion progression since last evaluation

If repeat imaging does not confirm PD per irRECIST as assessed by the investigator and the subject continues to be clinically stable, study treatment tumor imaging assessment may continue per study schedule.

Scenarios where PD is confirmed at repeat imaging if ANY of the following occurs by irRECIST:

- Target lesion sum of diameters remain $\geq 20\%$ and at least 5 mm absolute increase compared to nadir
- Non-target disease resulting in initial PD is qualitatively worse
- New lesion resulting in initial PD is qualitatively worse
- Additional new lesion(s) since last evaluation
- Additional new non-target progression since last evaluation

If repeat imaging confirms PD due to any of the scenarios listed above, subjects will be discontinued from study therapy.

NOTE: If a subject has confirmed radiographic progression (i.e., 2 scans at least 4 weeks apart demonstrating progressive disease) per irRECIST, but the subject is achieving a clinically meaningful benefit and there is no further increase in the tumor burden at the confirmatory tumor imaging, an exception to continue treatment may be considered following consultation with the Sponsor. In this case, if treatment is continued, tumor imaging should continue to be performed following the intervals as outlined in Section 6.0 (Trial Flowchart) and be submitted to the central imaging vendor.

Additional details about irRECIST are referenced in Merck TIP Sheet for RECIST 1.1 and irRECIST.

Table 5 irRECIST Imaging and Treatment after First Radiologic Evidence of PD

	Clinically Stable		Clinically Unstable	
	Imaging	Treatment	Imaging	Treatment

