First radiologic evidence of PD by RECIST 1.1	Repeat imaging at ≥ 4 weeks at site to confirm PD	May continue study treatment at the Investigator's discretion while awaiting confirmatory scan by site	Repeat imaging at ≥ 4 weeks to confirm PD per physician discretion only	Discontinue treatment
Repeat scan confirms PD by irRECIST at the local site	No additional imaging required	Discontinue treatment (exception is possible upon consultation with Sponsor).	No additional imaging required	N/A
Repeat scan shows SD, PR or CR by irRECIST at the local site*	Continue regularly scheduled imaging assessments	Continue study treatment at the local site Investigator's discretion	Continue regularly scheduled imaging assessments	May restart study treatment if condition has improved and/or clinically stable per Investigator's discretion. Next tumor imaging should occur according to the regular imaging schedule outlined in the protocol.
* SD,PR and CR for irRECIST are identical to RECIST 1.1				

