A missed disease assessment includes any assessment that is not obtained or is considered inadequate for evaluation of response.		

Table 2 Censoring Rules for Analyses of PFS

Situation	Date of progression or censoring
No PD and no death; new anticancer treatment is not initiated	Censored at last disease assessment
No PD and no death; new anticancer treatment is initiated	Censored at last disease assessment before new anticancer treatment
PD or death documented after ≤ 1 missed disease assessment	Progressed at date of documented PD or death
PD or death documented after ≥ 2 missed disease assessments	Progressed at date of documented PD or death

An outline of the key efficacy analysis strategy is presented in [Table 3](#).

Table 3 Analysis Strategy for Key Efficacy Endpoints

Endpoint	Statistical Method	Analysis Population	Missing Data Approach

 • ORR by BICR per RECIST1.1 • ORR by investigator assessment per RECIST1.1 	Exact test of binomial parameter; 95% CI [†]	ASaT	Subjects with missing data are considered non-responders

 • DOR by BICR per RECIST1.1 • DOR by investigator assessment per RECIST1.1 	Summary statistics using Kaplan-Meier method	All responders	Refer to Table 1

 • PFS by BICR and investigator assessment per RECIST 1.1 	Summary statistics using Kaplan-Meier method	ASaT	Refer to Table 2

 • DCR by BICR and investigator assessment per RECIST 1.1 	Exact test of binomial parameter; 95% CI [†]	ASaT	Subjects with missing data are considered disease not controlled

 • OS 	Summary statistics using Kaplan-Meier method	ASaT	Censored at last known alive date
[†] 95% confidence interval is determined by the upper and lower 97.5% one-sided confidence bounds.			

The strategy to address multiplicity issues with regard to multiple endpoints and interim analyses is described in Section 3.7, Interim Analyses and in Section 3.8, Multiplicity.

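### irRECIST PFS counts only confirmed progression, but clinically unstable subjects need no confirming scan, so a first PD that is never re-scanned is not an event and this exploratory curve is biased upward

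*Combined protocol and SAP*

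**What the plan says.** **Event definitions.** sSAP 3.4.1 gives two PFS definitions that differ in one word. For RECIST 1.1 the endpoint is "the time from the first day of study treatment to the first documented disease progression or death due to any cause". For irRECIST by BICR, listed as exploratory, it is "the time from first day of study treatment to the first confirmed disease progression or death due to any cause".

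**Who is re-scanned.** Protocol 7.1.2.6.7 asks for a repeat scan at 4 weeks or later in clinically stable subjects. One of its four stability criteria is "Absence of rapid progression of disease"; the others concern symptoms, signs and laboratory values, ECOG decline, and tumour at critical sites. A subject deemed "clinically unstable should be discontinued from trial treatment at site-assessed first radiologic evidence of PD and is not required to have repeat imaging". Table 5 has the same rule for the unstable column: "Repeat imaging at ≥ 4 weeks to confirm PD per physician discretion only".

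**What ends imaging.** Protocol 7.1.2.6.2 stops study imaging at new anti-cancer therapy. Flow Chart (6.1) footnote b moves subjects to telephone contact after site-assessed progression or new treatment. Footnote q asks for a scan at discontinuation when the site has not confirmed PD, but waives it if one was taken in the previous 4 weeks.

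**Censoring.** sSAP Table 2 has four PFS rows, among them "No PD and no death; new anticancer treatment is initiated" (censored at the last assessment before that treatment) and "PD or death documented after ≥ 2 missed disease assessments" (event at the documented date). None covers an unconfirmed PD. sSAP Table 3 points to Table 2 for RECIST 1.1 PFS and has no row for irRECIST PFS. Protocol 8.6.1 leaves exploratory methods to the sSAP.

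**The concern.** Confirmation is there so that a PD later shown to be pseudoprogression is not counted. For that, a PD need only be set aside when a later scan contradicts it. The sSAP rule goes further: it also sets aside a PD that nobody looked at again. Missing confirmation is not random here, because the protocol waives the repeat scan for subjects whose condition is worsening. Their progression would be replaced by a later death date, or by censoring at about the moment of progression, which is informative.

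Protocol 4.2.3.2 justifies irRECIST on the ground that RECIST 1.1 may understate benefit. A reader who sets the two PFS curves side by side could take a gap as support for that view when part of it comes from progressions that were never re-scanned.

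**Working it through.** The documents give no expected value, event count or sample size for irRECIST PFS, so there is no planned figure to reproduce. I trace the rule first and then illustrate its size.

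**1. Two subjects with the same first PD at Week 9** (63 days / 30.4375 = 2.07 months)

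| | RECIST 1.1 PFS | irRECIST PFS, read literally |
|---|---|---|
| Stable, repeat scan at Week 13 confirms | event, Week 9 | event (Week 9 or 13; the sSAP does not say which) |
| Unstable, no repeat scan, new chemotherapy, dies at month 10 | event, Week 9 | event at month 10 |
| As above, alive at cut-off | event, Week 9 | no event; if Table 2 is borrowed, censored at about Week 9 |

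**2. Direction.** For each affected subject the observed time stays the same or lengthens, and the event may become a censoring. With no other censoring, the Kaplan-Meier curve is then at least as high at every time point.

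**3. Size in closed form.** Assumptions: exponential time to first PD with median m = 4 months, the middle of the 3 to 5 months that Protocol 4.1.1.1 cites for single-agent chemotherapy in platinum-resistant disease; a share u of PDs never confirmed; exponential survival after PD with median r. The probability that an unconfirmed subject has no event by t is

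G(t) = [m·2^(−t/m) − r·2^(−t/r)] / (m − r).

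At t = 6 months:

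- First PD always counted: 2^(−1.5) = 35.4%.
- r = 2: G = (4×0.3536 − 2×0.125)/2 = 0.582. The rate is (1−u)×0.3536 + u×0.582, which is 37.6% at u = 10% and 39.9% at u = 20%.
- r = 5: G = (5×0.4353 − 4×0.3536)/1 = 0.762. The rate is 39.4% at u = 10% and 43.5% at u = 20%.
- Censored at PD instead: the event hazard is multiplied by (1−u), so the rate is 2^(−1.5(1−u)), which is 39.2% at u = 10% and 43.5% at u = 20%.

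**4. Size on the trial's scan schedule.** Simulation of 200,000 subjects per scenario, with scans every 9 weeks to Week 54, then every 12 weeks, and a cut-off at 24 months. Assumed inputs: median time to progression 2, 3 or 5 months; u = 10%, 20% or 30%; median survival after PD 2 or 5 months; 0%, 50% or 100% of unconfirmed subjects censored at the PD scan rather than followed to death; median 30 months for death without progression. The reference counts each unconfirmed first PD as an event at its scan.

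| | Reference | Literal rule | Difference (points) |
|---|---|---|---|
| 6-month rate, mid case (3 months, u = 20%, 2 months, half censored) | 33.3% | 39.5% | +6.2 |
| 12-month rate, mid case | 6.9% | 10.0% | +3.1 |
| 6-month rate, all scenarios | – | – | +1.5 to +15.1 |
| 12-month rate, all scenarios | – | – | +0.7 to +11.0 |

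The median sticks to scan dates. It stays at 4.14 months in every 3-month scenario, rises from 2.07 to at most 4.14 in the 2-month scenarios, and goes from about 5 to 6.21 in the 5-month scenarios.

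For scale, Protocol Table 9 gives a 95% interval of 29.3% to 41.5% for a 35% proportion in 250 subjects, a half-width of about 6 points. The mid-case shift is of that order.

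**The case against.** Several objections stand and limit the point.

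- *A reader might infer that an unstable subject can never have a confirmed progression.* The documents do not support this. Table 5 allows a discretionary repeat scan and has rows for its result, and footnote q can produce a discontinuation scan. Only subjects with no later evaluable scan are affected.
- *A reader might take it as settled that sSAP Table 2 censors these subjects.* Table 3 ties Table 2 to RECIST 1.1 PFS only, and Table 2 speaks of PD without the word confirmed. Applying it to irRECIST PFS is an inference. The restriction to confirmed PD comes from the definition in sSAP 3.4.1, not from Table 2.
- *The site judges stability, while BICR reads the endpoint.* A site PD scan may confirm a PD that BICR called earlier, which removes the problem for that subject. The reverse also occurs: BICR may first call PD on the site's confirming scan, after which Table 5 requires no more imaging.
- *Unstable does not mean fastest progressing.* Rapid progression is one of four criteria.
- *Death remains an event.* Subjects who die soon after PD add little bias, as the scenarios with 2-month survival after PD and full follow-up to death show.
- *Protocol 7.1.2.6.7 refers to a separate sponsor tip sheet for irRECIST detail.* It is not among the documents and might address unconfirmed PD. Even so, the analysis rule belongs in the sSAP, which states none.

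**Conclusion.** The concern holds as a minor point on an exploratory endpoint. The stated event definition, combined with the imaging rules, leaves a first PD without a later evaluable scan uncounted, and the effect is to raise irRECIST PFS. Under the assumed inputs the 6-month rate rises by about 1.5 to 15 points, and the median may not change. The share of unconfirmed progressors and their survival after PD are assumptions; the documents give neither, so the true size is unknown.

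Two stronger conclusions should not be drawn. First, one might infer that the trial plans to measure what irRECIST adds over RECIST 1.1 and that this comparison is compromised. Exploratory objective 1 (Protocol 3.3) only asks to evaluate the irRECIST endpoints, and neither document plans a comparison of the two curves. Second, one might infer that the median could about double. In the closed-form model with m = 4, the median reaches 8.8 months only if 60% of PDs are never confirmed and those subjects then have a median survival of 7 months. Nothing in the documents supports that share, and 7 months is generous for subjects judged unstable.

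Primary ORR and secondary RECIST 1.1 PFS do not use this definition and are unaffected.

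**What to change.** In sSAP 3.4.1, define the irRECIST PFS event as death or the first BICR PD that either is confirmed at 4 weeks or later or has no later evaluable scan, dated at that first PD. Only a PD that a later scan refutes is then set aside. The same date rule settles which scan dates a confirmed PD.

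State which censoring rules apply to irRECIST PFS, either by extending Table 2 with a row for unconfirmed PD or in a separate table, and add the endpoint to Table 3. State the end-of-response rule for irRECIST DOR in the same terms, since the sSAP currently gives none. Report the strictly confirmed-only definition as a sensitivity analysis, with the number of first PDs that had no later evaluable scan, so that the reader can see the size of the effect.

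This takes a few lines of text and a small change to the derivation code. It needs no new data and no change to imaging or treatment rules. The price is a slightly less favourable irRECIST PFS.
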